## 5.5 Randomization and Blinding

### 5.5.1 Randomization

All eligible subjects will be screened for enrollment. All eligible and consented subjects will be randomized into 1 of 2 treatment groups in a ratio of 1:1. Randomization will be performed using an Interactive Response Technology (IRT) system.

Randomization will occur ONLY after the subject has signed the informed consent, has been enrolled into the study, and has met all Inclusion and Exclusion criteria. Study drug should be started after randomization during the Run-in visit.

#### Interactive Response Technology (IRT)

Selected individuals at each study center, along with subjects, will be authorized by pre-coded identification numbers to have password protected access to the designated portions of the system. Authorized individuals will interact with the IRT in accordance with the user manual. The IRT will be used by the site to assign subjects randomization numbers, dosing cohorts, and drug/device supplies.

The IRT will also be used for functions such as: accountability (by site and subjects), dispensing, reordering or replacement of INOpulse device, cartridges or ancillary supplies, programming of INOpulse devices, and emergency unblinding of subject treatment.

### **5.5.2 Blinding**

All study drug cartridges will be labeled with informative language that each cartridge contains up to 6.0 mg/L (4880 ppm) NO gas to allow for compliance with compressed gas transportation regulations while maintaining a blinded label. All study labels will indicate the kit number and all drug cartridges will be labeled with a blinded unique identification number prior to shipment to the investigative site or the subject's home. Drug cartridges are intended for use by a single subject who will be assigned the corresponding kit number on the study label by the IRT. Similarly, all devices will be uniquely identified, and tracked and controlled by the IRT.

#### **Breaking of Blinded Codes**

The blind could be broken only if specific urgent treatment would be dictated by knowing the treatment status of the subject. In such cases, the Investigator or designee will be able to call or login to the IRT to unblind a subject. It is strongly recommended to discuss the case with the Sponsor's medical monitor before unblinding.

The date, time, and reason for the unblinding must be documented in the eCRF, and the Sponsor's medical monitor must be informed as soon as possible.

## **6.0 Data Considerations**

### **6.1 Protocol Violations**

The following protocol violations will be considered major violations and will lead to the exclusion of subjects from the Per-Protocol (PP) analysis set. This list is not exhaustive and will be expanded at the discretion of the study team.

- Major Protocol Violations.
- Subjects whose compliance to study product and/or study procedures have been insufficient.
- Details of all the protocol deviations will further be elaborated in separate protocol deviation specification document.

Summary table by treatment group for number of subjects encountering protocol violations will be produced.

### **6.2 Product Compliance (Device Adherence)**

Subjects will be supplied with products at randomization visit. The product adherence data is not captured on CRF and will be supplied via the IRT by Y Prime.

The following fields are agreed.

- Patient number
- Report Start Date
- Report End Date
- Day of Usage
- Number of Minutes of Use
- Average Usage for Period

The subject will be deemed compliant if their average daily usage is more than 12 hours.

### 6.3 Handling of Missing Data

#### Missing data imputation for primary endpoint:

For primary analysis, i.e. change from baseline at Week 18, missing data will not be imputed.

The following missing data imputation techniques will be employed for sensitivity analyses of primary endpoint.

- 1) Last Observation Carry Forward (LOCF) approach will be applied for subjects not withdrawing trial due to adverse events, for subjects withdrawing trial due to adverse events (including deaths), worst value (for e.g. zero for 6MWD) will be assigned at 18 weeks visit.
- 2) Worst-case imputation approach I (i.e. impute the missing value for a subject with worst value (within the subject) for all subjects who withdraw prematurely for any reason. The value of zero for 6MWD will be imputed for all deaths.
- 3) Worst-case imputation approach II (i.e., impute the missing value for a subject in the active and Placebo dose group by the worst result of all subjects with non-missing assessments in their respective assigned dose groups). The value of zero for 6MWD will be imputed for all deaths.
- 4) Worst-case imputation approach III (i.e. impute the missing value for a subject in the active dose group by the worst result of all subjects with non-missing assessments in the same active dose groups and impute the missing value for a subject in placebo group by his/her last available assessment prior to the missing assessment. The value of zero for 6MWD will be imputed for all deaths.

#### Missing data imputation for secondary endpoint:

For all the other efficacy endpoints, the last observation carry forward (LOCF) approach will be used in handling the missing data as that used in the EARLY study ([Galiè 2008](#)).

### 6.4 Baseline Definition

The Week 2 assessment is considered as baseline for all the efficacy analyses. For SF-36, week 0 assessment is used as baseline.

## 7.0 Statistical Considerations

For statistical analysis reporting, all categorical (or discrete) variables will be summarized with frequency counts and percentage, and continuous variables will be summarized showing mean, geometric mean (appropriate for log transformed variables), standard deviation, median, minimum and maximum. Within each cell of a summary table, number should be integer, and percentage should be rounded with one decimal point. Mean and median should be rounded to one decimal point, minimum and maximum may be integer, but can have no more than one decimal point. A standard deviation or standard error should be rounded to two decimal points.

The p-value will be in the format of “#.xxx”, in which “#” stands for 0 or 1 and “xxx” for any numbers from 0 to 9 each. If “#” is “1”, “xxx” must be “000”. However, if the p-value is less than 0.001, it will be indicated “< 0.001” instead.

Decimal points as recorded in the database should be used to calculate any derived variable/s. rounding for significant digits, if applicable, will be applied only after the analysis has been performed.

### 7.1 Definition of Analysis Sets

All study data will be analyzed using the subjects’ populations as defined below.

#### 7.1.1 Enrolled Analysis Set

All subjects enrolled in the study will comprise of enrolled population. There will be no safety or efficacy analysis performed on this set.

#### 7.1.2 Randomized Analysis Set

All subjects randomized in the study will comprise of randomized population.

#### 7.1.3 Intent to Treat (ITT) Analysis Set

The ITT analysis set will include all randomized subjects who remained eligible after the Run-in period. It will compare the treatment groups on the basis of randomized treatment rather than treatment actually received.

#### 7.1.4 Modified Intent to Treat (mITT) Analysis Set

The mITT analysis set will include all randomized subjects who remained eligible after the Run-in period and have more than average 12 hours of device usage. It will compare the treatment groups on the basis of randomized treatment rather than treatment actually received.

#### 7.1.5 Per-Protocol (PP) Analysis Set

The Per Protocol (PP) analysis set will consist of all subjects included in the ITT population who adhere to all protocol requirements without causing any major violation. Major protocol violations are defined in section 6.1 of SAP.

Primary population for the analysis is ITT. Primary analysis will also be performed on PP analysis set.

#### 7.1.6 Safety Analysis Set

The safety analysis set will include all randomized subjects who received the study treatment. Safety analysis will be based on the treatment actually received and not randomized.

### 7.1.7 Modified Safety Analysis Set

The safety analysis set will include all randomized subjects who received the study treatment and became eligible after run in period. Safety analysis will be based on the treatment actually received and not randomized.

Adverse events (AEs and SAEs) and concomitant medication data will be analysed and summarized based on Safety Analysis set and Modified Safety analysis set.

## 7.2 Evaluation of Baseline and Demographic Characteristics

### 7.2.1 Screening

All screening variables will be summarized on enrolled population.

### 7.2.2 Demographic

All demographic characteristics variables as captured on CRF will be summarized on randomized population and ITT.

These characteristics will also be summarized for following subgroups:

- 1) Continuous positive airway pressure (CPAP),
- 2) Bilevel positive airway pressure (BiPAP)

### 7.2.3 Baseline Variables

All the baseline characteristics variables as captured on CRF will be summarized on randomized population and ITT. Baseline characteristics will also be summarized for subjects discontinuing before 18 weeks.

These characteristics will also be summarized for following subgroups:

- 1) Continuous positive airway pressure (CPAP),
- 2) Bilevel positive airway pressure (BiPAP)

## 7.3 Primary analysis

### 7.3.1 Change in 6MWD

The primary endpoint for double blinded of study is change from baseline in 6MWD at Week 18.

The average of the two 6MWDs at Week 2 (after run-in) will be used as the baseline value.

This endpoint is collected at all the visits including screening.

The change from baseline in 6MWD will be analysed using Mixed Model Repeated Measures (MMRM) (Table 23).

**Table 23 Factors/Covariates for Analysis**

Factor/Covariates	Random/Fixed	Type
-------------------	--------------	------

Factor/Covariates	Random/Fixed	Type
Treatment Group	Fixed	Categorical(Two)
Visit	Fixed	Categorical(Four)
Prostanoids usage status	Fixed	Categories(Two)
Baseline 6MWD	Fixed	Continuous
Treatment By Visit Interaction	Fixed	Categorical (Eight)

### Hypothesis:

$H_0: \mu_{iNO\ 75} = \mu_{Placebo}$  versus  $H_1: \mu_{iNO\ 75} > \mu_{Placebo}$  for at least one realization.

The following treatment comparisons will be assessed on change from baseline.

- 1) *iNO 75 mcg/kg IBW/hr versus matching Placebo (Primary interest) at Week 18.*

### Missing Data Imputation Rules:

Missing data will not be imputed for primary analysis.

The results will be presented in terms of LS means and the difference between LS means, with associated confidence interval and p-value.

Standard descriptive statistics for two separate categories ((1) increase in 6MWD from baseline at Week 18 and decrease in 6MWD from baseline at Week 18) will be presented along with the visit-wise 6MWD.

This analysis will be performed on Intention to treat (ITT), Per-Protocol (PP) and Modified Intention to treat (mITT).

Analysis performed on ITT will be considered as primary.

The within-subject error is assumed to have an unstructured (UN) covariance matrix. However, if the fit of the unstructured (UN) covariance structure fails to converge, then the following options will be tried in order until convergence is reached.

- 1) Toeplitz with Heterogeneity (TOEPH)
- 2) Autoregressive with Heterogeneity (ARH(1))
- 3) Toeplitz (TOEP)
- 4) Autoregressive (AR(1))
- 5) Compound Symmetry (CS)

If model still doesn't converge then this will be highlighted and discussed in the BDR meeting and an appropriate covariance structure to be used will be agreed. The denominator degrees of freedom will be estimated using a Kenward-Roger approximation. The pairwise treatment differences will be estimated as differences between the least-squares means and tested using an F-test based on the Type III sums of squares.

The SAS code for the MMRM analysis is provided below for interim analysis.

**PROC MIXED Data= 6MWD;**

**CLASS PATID TREAT STRATA VISIT;**

**MODEL CHG = 6MWDBASE TREAT STRATA VISIT TREAT\*VISIT / DDFM=KR OUTPRED=RESID;**

**REPEATED VISIT / SUBJECT=PATID (TREAT) GROUP = TREAT type=UN;**

**LSMEANS TREAT\*VISIT / PDIFF cl;**

**ODS OUTPUT DIFFS=DIFFS1;**

**ODS OUTPUT LSMEANS=LSMEANS1;**

**RUN;**

If the blinded data is used to determine the sample size then Z statistics by CHW will not be used. This decision will be taken before interim analysis.

If the unblinded data is used to determine the sample size then Z statistics by CHW will be used.

For final analysis the Z statistics will be calculated using the CHW method (Cui L, Hung HM, Wang SJ, 1999).

If the sample size does not increase, the test statistics at the final analysis, denoted by  $Z_N$  is weighted sum of the test statistics from the two stages  $Z_n$  (Test statistics at interim) and  $Z_{N-n}$  ([Menon and Zinc](#)).

$$Z_N = \sqrt{\frac{n}{N}} Z_n + \sqrt{\frac{N-n}{N}} Z_{N-n}$$

If after interim analysis, the sample size is increased to M ( $M > N$ ) per group, the same statistic becomes: .

$$Z_M = \sqrt{\frac{n}{N}} Z_n + \sqrt{\frac{M-n}{M}} Z_{M-n}$$

This may inflate the type one error and hence CHW proposed a new test statistics as follows:

$$Z'_M = \sqrt{\frac{n}{N}} Z_n + \sqrt{\frac{N-n}{N}} Z_{M-n}$$

### **Pooling of centers:**

NA.

**Direction of Difference:** Higher is better.

Positive difference in LS means (*iNO 75 mcg/kg IBW/hr versus matching Placebo*) for change from baseline in 6MWD at Week 18.

### **Heteroscedasticity Assumption:**

The square of residuals will be modelled using PROC MIXED and overall F test will indicate the presence or absence of heteroscedasticity.

### **Normality Assumption:**

Normality assumption for Change from baseline in 6MWD will be assessed using the following:

1. Shapiro-Wilk statistics and
2. Visual examination of Q-Q plots.

PROC UNIVARIATE procedure in SAS will be used to check for the normality assumption. The normal probability plot (normal Q-Q plot) of residuals will also be generated and used to assess the normality. If

the residuals generated come from normal distribution then the normal probability plots should approximate straight lines.

Following SAS code will be used to generate Wilk's Shapiro and Q-Q plots.

```
PROC UNIVARIATE Data= Residual  NORMAL;
VAR RESID;
QQPLOT RESID /NORMAL (MU=EST SIGMA=EST COLOR=RED L=1);
RUN;
```

Normality results will be discussed during model diagnostics post unblinding and analysis approach will be finalized.

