16.2. Sample Size Determination

Interim Analysis will be conducted by an independent DMC after 18-week 6MWD data are available from 75 patients. The purpose of the interim analysis is to stop the trial for an early efficacy or futility conclusion or to continue the trial to 150 or 188 - patients (total randomized is higher to account for an anticipated 20% dropout rate). Group sequential early stopping criteria and sample size re-estimation methodology are further described in the statistics section of this protocol. They are constructed to control overall type 1 error at 0.025, 1-sided. Simulations assuming true underlying mean treatment difference in 6MWD ranging from 30-70 meters and standard deviations from 50 to 75 meters yielded >87% power for all cases except the most extreme case (mean difference 30 meters and SD 75), for which power was ~71%.

Subjects who do not comply with the required device adherence, as well as who do not meet the study entry criteria at Week 2, will be withdrawn from the study.

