16.3. Efficacy Analyses

16.3.1. Primary Efficacy Endpoint

The primary endpoint is to evaluate the efficacy of iNO as measured by the placebo-adjusted change in 6-minute walk distance (6MWD) from baseline to 18 weeks. The average of the two 6MWDs at Week 2 (after run-in) will be used as the baseline value for analysis of data. The

6MWD at Week 2 should be obtained on all subjects, even if the subject does not qualify to enter into the treatment phase.

The primary statistical test for the primary endpoint will be performed using a repeated measures mixed model with the baseline stratification factor (i.e., the prostanoid usage status), - treatment arm, week, and treatment-by-week interaction as the main effects. As a covariate, baseline 6MWD assessment will be included in the model. In case the normality assumption is substantially violated (i.e., graphical assessment of residuals from the analysis model and the Shapiro-Wilk test statistic graphical assessment of the residuals from the analysis model and), the primary efficacy endpoint will be analyzed using the van Elteren test stratified by the prostanoid usage status. Least Squares mean differences, standard errors, 95% confidence intervals will be derived from the analysis model.

Exploratory analyses will be performed to evaluate the effects of demographics and baseline characteristics on the efficacy response with appropriate statistical methods. Subgroup analyses based on study drug usage, background therapies, demographics and baseline characteristics, as well as other study compliance status will be conducted. Additional statistical methods such as mixed effects model and Cochran–Mantel–Haenszel (CMH) test (for dichotomized response analysis) may be utilized in the exploratory analyses.

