#### **Analysis of Non-Normal Data:**

In case of normality issues, the analysis will be performed using van Elteren test for stratified response (change from baseline).

The SAS code applied as follows:

```
Proc Npar1way data=data;
```

```
  Strata strata;
```

```
  Class treatment;
```

```
  Var change;
```

```
Run;
```

In case, we encounter normality issues, the results needs to be interpreted accordingly.

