11	The Change from baseline analyzed using the same model as primary on ITT population for all subjects on at least two oral treatment (no IV, Inhaled and SC) of either prostacyclin or Endothelin Receptor Antagonists (ERAs) or Phosphodiesterase Inhibitors (PDE 5 Inhibitors)
12	
If the normality and homogeneity of variance assumptions are significantly violated, then the baseline and change from baseline parameters are first ranked separately, using the combined data from all treatment groups. Tied values will receive the mean value (midranks) of the corresponding ranks.
 
The primary analysis MMRM model on ranked values will be performed on ITT population.

13	Responder analysis for patients achieving $\geq 30$ meters 6MWD response from baseline at Week 18 will be performed using the proportions test on ITT population
14	Change from Baseline in 6MWD analyzed using the same model as primary for all subjects having concurrent use of INOpulse device with a continuous positive airway pressure (CPAP), bilevel positive airway pressure BiPAP, or any other positive pressure device.

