**Table 35: Interim and Final Analysis Rules:**

Category	Rule
Efficacy	At interim analysis (after 75 patients), if the one-sided $p < 0.0046$ then the study will stop for efficacy (Wald Statistics)
Efficacy	At final analysis (after 150 patients or 188 patients depending on CP and PP), if the one-sided $p < 0.0229$ then the study will yield an efficacy conclusion. (based on CHW Statistics)
Futility	At interim analysis, if conditional power (CP) or predictive power (PP) $\leq 10\%$ then the study stops for futility.
Continue	At interim analysis, if $10\% < CP$ and $PP < 57.2\%$ then trial continues to 150 patients.
SSR	At interim analysis, if $57.2\% \leq CP$ or $PP < 80\%$ the sample size is increased to $N=188$ . The lower bound of the promising zone interval was calculated based on the minimum treatment effect needed to achieve 70% or higher CP.
Continue	At interim analysis, if $CP$ and $PP \geq 80\%$ and 1-sided $p > 0.0046$ , then the trial continues to $N = 150$ patients.

This is the "promising zone" sample size re-estimation (SSR) design of [Mehta & Pocock \(2011\)](#), which uses the [Cui, Hung, Wang \(1999\)](#) method of analysis to combine the test statistics for the separate analyses of the IA and post-IA parts of the trial, if the trial does not stop at IA.

The final analysis is via weighted Z statistic using equal weights for the IA and post IA test statistics. It requires  $p < 0.0229$  1-sided for statistical significance to control the overall type 1 error level at 0.025 1-sided with  $\gamma = -3$  error spending function ([Hwang, Shih, deCani 1990](#)).

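### The normality check that can move the primary 6MWD analysis from MMRM to van Elteren is coded on pooled raw residuals, so Shapiro-Wilk over-rejects when the MMRM's own assumptions hold

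*SAP*

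**What the plan says.** **Model.** SAP 7.3.1 analyses change in 6MWD with an MMRM over four post-baseline visits (Table 23). The code reads "REPEATED VISIT / SUBJECT=PATID (TREAT) GROUP = TREAT type=UN", so each arm has its own unstructured covariance matrix. The MODEL statement saves residuals with `OUTPRED` and requests no scaling.

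**Check.** Under Normality Assumption the SAP names two inputs, Shapiro-Wilk and Q-Q plots, and states "PROC UNIVARIATE procedure in SAS will be used to check for the normality assumption". The code has `VAR RESID` and `QQPLOT RESID`, with no BY or CLASS statement. Results are discussed after unblinding, and the analysis approach is settled then. Protocol 16.3.1 names the same inputs, "graphical assessment of residuals from the analysis model and the Shapiro-Wilk test statistic", and requires a substantial violation. Neither document gives a numerical cut-off.

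**Consequence.** SAP 7.3.1, Analysis of Non-Normal Data: "In case of normality issues, the analysis will be performed using van Elteren test". Protocol 16.3.1 makes the same switch.

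**Variance check.** A separate paragraph models squared residuals and says the "overall F test will indicate the presence or absence of heteroscedasticity". It attaches no action to the result. Variance homogeneity reappears only in Table 24, item 12, which begins "If the normality and homogeneity of variance assumptions are significantly violated" and leads to a sensitivity MMRM on ranks.

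**The concern.** The question for the check is whether the residuals are normal under the fitted model. That model does not say the residuals are independent or share one variance. The Shapiro-Wilk reference distribution requires both. The code therefore tests a narrower null than the one the primary analysis rests on, and that null can fail while the MMRM is entirely correct.

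The Q-Q plot is drawn from the same column against a single normal line. Pooling normal residuals of unequal variance gives a heavier-tailed mixture, so the plot is not an independent safeguard.

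What is at stake is the choice of primary analysis in a confirmatory trial. The van Elteren code ranks one change value per subject within prostanoid strata. It has no baseline covariate and no use of earlier visits, and it gives no LS mean difference with a confidence interval, which both documents promise.

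**Working it through.** **1. Inputs from the documents.** 150 evaluable subjects and 20% drop-out (SAP 5.4): 150 / (1 − 0.20) = 187.5, rounded up to 188, which matches the plan. Four visits (SAP Table 23), so at most 188 × 4 = 752 residuals. Planning SDs are 50 to 75 m (Protocol 16.2). Phase 2 subgroup SDs are 42 m (iNO 75) and 32 m (placebo) (Protocol 5.1), a ratio of 42/32 = 1.31. The plan gives no error rate for the normality check, so there is no stated figure to reproduce for it.

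**2. Inputs assumed.** Within-subject correlation (compound symmetry, CS, at 0, 0.5 or 0.8; AR(1) at 0.7), the pattern of SD over visits, drop-out completely at random, and a 5% level.

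**3. Why correlation alone matters.** With equal SDs the pooled residuals are still marginally normal, but their sample shape varies more than independence implies. For four visits the variance of sample skewness is multiplied by f = (1/4) Σ ρ_ij³, summed over all visit pairs (complete data, estimation of means ignored). A nominal 5% skewness test then rejects with probability P(|Z| > 1.96/√f):

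| Correlation | f | Rejection |
|---|---|---|
| CS 0.5 | 1 + 3(0.5³) = 1.375 | 9.5% |
| AR(1) 0.7 | 1 + ½[3(0.7³) + 2(0.7⁶) + 0.7⁹] = 1.652 | 12.7% |
| CS 0.8 | 1 + 3(0.8³) = 2.536 | 21.8% |

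Shapiro-Wilk is not a skewness test, but it should be inflated to a similar degree.

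**4. Why unequal variances matter.** An equal mixture of two normals with SDs 32 and 42 has excess kurtosis 3[(42² − 32²)/(42² + 32²)]² = 3(740/2788)² = 0.21. The standard error of kurtosis for 752 independent normal values is √(24/752) = 0.18. The mixture therefore sits about 1.2 standard errors from normal on average, with no departure from the model.

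**5. Simulation.** Data were exactly multivariate normal, with 188 subjects, the SAP model fitted with an unstructured covariance per arm, and 800 trials per case. The Monte Carlo standard error is √(0.05 × 0.95/800) = 0.8 points at 5% and √(0.5 × 0.5/800) = 1.8 points at 50%.

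| SD pattern | Pooled raw Shapiro-Wilk, p < 0.05 |
|---|---|
| Equal, correlation 0 (calibration) | 5.4% |
| Equal, CS 0.5 | 7.7% |
| Equal, AR(1) 0.7 | 13.0% |
| Equal, CS 0.8 | 25.6% |
| Arms 32/42, flat over visits | 15% to 39% |
| Visits rising 50 to 75, arms equal | 19% to 32% |
| Visits rising 50 to 75, arm ratio 1.31 | 42% to 53% |

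Separate simulations gave 11% and 15% to 17% for AR(1) 0.7 with equal arm SDs, and 30% for CS 0.8. With AR(1) 0.7 and the 42/32 ratio they gave 26% (visit SDs 50 to 60), 45% (visit SDs 40 to 60), and a range of 24% to 48%.

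**6. Interim size.** The SAP introduces its MMRM code as code for the interim analysis. At 75 subjects and CS 0.8 the pooled test rejected in 25% to 33% across the first four SD patterns simulated. The documents do not say whether the check is applied then.

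**7. After the correction.** Across all 188-subject cases, Shapiro-Wilk on Cholesky-scaled residuals rejected in 3.0% to 6.9%, and on Week 18 residuals standardised within arm in 2.4% to 5.9%.

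**The case against.** **A rejection is not a switch.** This is the strongest reply, and it stands. Protocol 16.3.1 asks for a substantial violation, the Q-Q plot is an equal input, and people decide. In simulations with AR(1) 0.7 the mean W was 0.997 with equal SDs, 0.996 in the 26% case and 0.995 in the 45% case, against 0.997 for independent normal data. The mean Q-Q correlation was 0.997 to 0.999 throughout. A reader of those plots would often see no reason to leave the MMRM. It would be tempting to infer that the trial abandons its primary analysis in 15% to 50% of cases, but the documents do not support that.

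**The power cost is small on average.** At 30 m and SD 60, one simulation gave 79% to 85% for van Elteren and 87% to 91% for MMRM, a gap of 6 to 8 points. That compares always switching with never switching. If every p < 0.05 forced a switch, the rough expected loss is excess rejection times the gap. That is (0.11 − 0.05) × 6 to 8 = 0.4 to 0.5 points, (0.26 − 0.05) × 6 to 8 = 1.3 to 1.7 points, or (0.45 − 0.05) × 6 to 8 = 2.4 to 3.2 points.

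**The higher rates rest on assumptions.** The documents give no within-subject correlation or visit-specific SDs. The 42/32 ratio is from a small post-hoc subgroup. If that is the group of 13 treated and 7 controls under SAP Table 22, a variance ratio of 1.72 on 12 and 6 degrees of freedom (two-sided p about 0.52) is no evidence of unequal arms. The correlation effect does not need that ratio.

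**The code path is partly inferred.** The MMRM writes a data set named RESID and PROC UNIVARIATE reads one named Residual; the step between is not shown. Pooling is the natural reading of the code as printed.

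**The squared-residual F test.** A reader might infer that it too can displace the MMRM. It cannot: only normality leads to van Elteren. Its residual type and model terms are not stated. When it rejects because variances differ, it is detecting a real feature. Deleting it is not clearly right either, since three fallback structures in SAP 7.3.1 (TOEP, AR(1), CS) assume constant variance over visits.

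**Conclusion.** The point holds for Shapiro-Wilk and, through the shared column, for the Q-Q plot. As coded, the check is not calibrated to the model it checks. At 188 subjects and a nominal 5% level, false signals run at about 11% to 30% with equal SDs and correlations of 0.7 to 0.8, and about 8% at compound symmetry 0.5. With the 42/32 arm ratio, alone or with modest growth in visit SDs, they run at about 15% to 50%.

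The direction follows from the model and the code; the size depends on the assumed correlations, SDs and level. These figures measure how often a misleading statistic reaches the people deciding. They do not measure how often the analysis changes, and nothing here measures an effect on the type 1 error. The missing cut-off and the post-unblinding timing are separate matters, and fixing either would still leave a miscalibrated statistic. The correction is worth making because the check bears on the choice of primary analysis and costs almost nothing to repair.

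**What to change.** In SAP 7.3.1, do one of the following:

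- add `VCIRY` to the PROC MIXED MODEL statement and use the scaled residual, confirming that the named output data set carries it; or
- keep only the Week 18 residual, one per subject, divided by its arm-specific SD.

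Then point both `VAR` and `QQPLOT` in the PROC UNIVARIATE code at that variable, align the data set names, and say in the text which residual is used. Leave the squared-residual F test and the trigger in Table 24, item 12, as they are for this purpose. The cost is a few lines of SAS and one sentence of SAP text, with no new data, visits or subjects.
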